10.10 Maintenance of Source Documents and Recordkeeping Requirements

As stipulated by 21 CFR §312.57 and ICH E6 GCP Consolidated Guidance Section 8, the Investigator or designee will maintain source documentation for this clinical study that documents the treatment and study course of subjects as described in the study manual. Source documents are original documents, data, and records from which the subject's eCRF data are obtained. These include, but are not limited to hospital records, clinical and office charts, laboratory and pharmacy records, diaries, microfiches, radiographs, and correspondence.

The Investigator and study staff are responsible for maintaining a comprehensive and centralized filing system of all study related (essential) documentation, suitable for inspection at any time by representatives from the Sponsor and/or applicable regulatory authorities.

The Investigator must retain all essential documents for this clinical study until at least 2 years after the last approval of a marketing application in an ICH region and until there are no pending or contemplated marketing applications in an ICH region, or until at least 2 years have elapsed since the formal discontinuation of clinical development of the study drug. However, the Investigator may need to retain these documents for a longer period, if required by the applicable regulatory requirements or by an agreement with the Sponsor. The Sponsor representative will be responsible for informing the Investigator and study site regarding when they no longer need to retain these documents. No records may be destroyed without the written approval from the Sponsor.

10.11 Long-term Retention of Samples for Additional Future Research

Blood and urine specimens will be collected and stored for additional analyses. These samples will be retained for long-term storage by the Sponsor and described in the ICF.

Any blood sample collected according to the schedule of assessments (**Table 1**) may be analyzed for any of the tests outlined in the protocol and for any tests necessary to minimize risks to study subjects. This includes testing to ensure that analytical methods produce reliable and valid data throughout the course of the study. It may also include, but is not limited to, investigation of unexpected results, incurred sample reanalysis, and analyses for method transfer and comparability.

All samples and associated results will be coded prior to being shipped from the site for analysis or storage. Samples will be tracked using a unique identifier that is assigned to the samples for the study. Results are stored in a secure database to ensure data integrity and control.

If permitted by local law and if informed consent is provided by the subject, the Sponsor may do additional testing on remaining samples (i.e., residual and back up) to investigate and better understand the disease and the dose response and/or prediction of response to the study drug. Results from this analysis are to be documented and maintained but are not necessarily reported as part of this study. Samples may be retained for up to 20 years.

Since the evaluations are not expected to benefit the subject directly or to alter the subject's treatment course, the results of these exploratory studies are not placed in the subject's medical record and are not to be made available to the subject, members of the subject's family, the subject's personal physician, or other third parties, except as specified in the ICF.

The subject retains the right to request that the sample material be destroyed by contacting the Investigator. Following the request from the subject, the Investigator is to provide the Sponsor with the required study and subject number so that any remaining blood samples and any other components from the cells can be located and destroyed.

Information collected from samples prior to the request for destruction will be retained by the Sponsor. The Sponsor is the exclusive owner of any data, discoveries, and derivative materials from the sample materials and is responsible for the destruction of the sample(s) at the request of the subject through the Investigator, at the end of the storage period or as appropriate (e.g., the scientific rationale for experimentation with a certain sample type no longer justifies keeping the sample). If a commercial product is developed from this research project, the Sponsor owns the commercial product. The subject has no commercial rights to such product and has no commercial rights to the data, information, discoveries, or derivative materials gained or produced from the sample.

10.12 Publication Policy

The institution and Investigator agree not to publish the results of this study without the prior written consent of the Sponsor. As used herein, the term ‘publish’ shall include oral presentations, written abstracts, written poster presentations, and written manuscripts or reviews, etc.

12. APPENDICES

12.1 List of Abbreviations and Definition of Terms

The following abbreviations and specialist terms are used in this study protocol.

Abbreviation/Term	Definition
ACEi	Angiotensin-converting enzyme inhibitor
ACTH	Adrenocorticotrophic hormone
ADL	Activities of daily living
AEs	Adverse events
AESI	Adverse events of special interest
AHT	Anti-hypertensive treatment
ALT	Alanine aminotransferase
ANCA	Anti-neutrophil cytoplasmic antibody
ANCOVA	Analysis of covariance
AOBP	Automated office blood pressure
ARB	Angiotensin receptor blocker
ASI	Aldosterone synthase inhibitor
AST	Aspartate aminotransferase
AUC	Area under the curve
BP	Blood pressure
BMI	Body mass index
BUN	Blood urea nitrogen
CBC	Complete blood count
CDC	Center for Disease Control and Prevention
CFR	Code of Federal Regulations
CHF	Congestive heart failure
CI	Confidence intervals
CKD	Chronic kidney disease
CKD-EPI	Chronic Kidney Disease Epidemiology Collaboration
C _{max}	Maximum observed plasma concentration
COVID-19	Coronavirus disease 2019
CRIC	Chronic Renal Insufficiency Cohort
CVD	Cardiovascular disease
CYP3A4	Cytochrome P450 3A
CYP11B2	Cytochrome P450 11B2 (aldosterone synthase)
DB	Double blind
DBP	Diastolic blood pressure
DMC	Data monitoring committee
ECG	Electrocardiogram
eCRF	Electronic case report form
EDC	Electronic data capture
eGFR	Estimated glomerular filtration rate
ENaC	Epithelial sodium channel
EoS	End of study

Abbreviation/Term	Definition
EOT	End of treatment
ESRD	End stage renal disease
EW	Early withdrawal
FAS	Full analysis set
FDA	Food and Drug Administration
FSH	Follicle-stimulating hormone
GCP	Good clinical practice
GLP1-RA	Glucagon-like peptide-1 receptor agonist
HbA1c	Glycosylated hemoglobin
HBr	Monohydrobromide
HRT	Hormonal replacement therapy
hsCRP	High-sensitivity C-reactive protein
IB	Investigator's brochure
ICF	Informed consent form
ICH	International Council for Harmonisation
IEC	Independent Ethics Committee
IMP	Investigational medicinal product
IND	Investigational new drug
IRB	Institutional review board
ITT	Intent-to-treat
KIM-1	Kidney injury molecule-1
LAR	Legally acceptable representative
LDH	Lactate dehydrogenase
LP	Lorundrostat-placebo
MAD	Multiple ascending dose
MCH	Mean corpuscular hemoglobin
MCHC	Mean corpuscular hemoglobin concentration
MCV	Mean corpuscular volume
MedDRA	Medical dictionary for regulatory activities
MLS-101 (lorundrostat)	A selective aldosterone synthase inhibitor
MMRM	Mixed model for repeated measurements
MR	Mineralocorticoid receptor
MRA	Mineralocorticoid receptor antagonist
NGAL	Neutrophil gelatinase-associated lipocalin
NSAIDs	Nonsteroidal anti-inflammatory agents
NTproBNP	N-terminal (NT)-pro hormone BNP
NYHA	New York Heart Association
OLE	Open label extension
PI	Principal Investigator
PK	Pharmacokinetic
popPK	Population pharmacokinetics
PL	Placebo-lorundrostat
PPIs	Proton pump inhibitors
PRA	Plasma renin activity

Abbreviation/Term	Definition
PT	Preferred term
QD	Once daily
RAAS	Renin-angiotensin-aldosterone system
RBC	Red blood cell
RH	Resistant hypertension
RTSM	Randomization and trial supply management
SAD	Single ascending dose
SAE	Serious adverse event
SAF	Safety analysis set
SAP	Statistical analysis plan
SBP	Systolic blood pressure
SGLT2i	Sodium-glucose cotransporter 2 inhibitor
SOC	System organ class
SRM	Study reference manual
T2DM	Type 2 diabetes mellitus
TEAE	Treatment-emergent adverse event
UACR	Urinary albumin to creatinine ratio
ULN	Upper limit of normal
UNS	Unscheduled visit
US	United States
WBC	White blood cells
WOCBP	Women of childbearing potential

12.4 Contraceptive and Barrier Guidance

12.4.1. Definitions

Women of Childbearing Potential (WOCBP)

A woman is considered fertile following menarche and until becoming postmenopausal unless permanently sterile (see below).

Women in the following categories are not considered WOCBP:

1. Premenarchal.
2. Premenopausal female with 1 of the following:
 - Documented hysterectomy
 - Documented bilateral salpingectomy
 - Documented bilateral oophorectomy

Note: Documentation can come from the site personnel's review of the subject's medical records, medical examination, or medical history interview.

3. Postmenopausal female:
 - A postmenopausal state is defined as no menses for 12 months without an alternative medical cause. A high follicle-stimulating hormone (FSH) level in the postmenopausal range may be used to confirm a postmenopausal state in women not using hormonal contraception or hormonal replacement therapy (HRT). However, in the absence of 12 months of amenorrhea, a single FSH measurement is insufficient.
 - Females on HRT and whose menopausal status is in doubt will be required to use one of the non-hormonal highly effective contraception methods if they wish to continue their HRT during the study. Otherwise, they must discontinue HRT to allow confirmation of postmenopausal status before study enrollment.

12.4.2. Contraception Guidance

Investigators should counsel WOCBP and male subjects who are sexually active with WOCBP on the importance of pregnancy prevention and the implications of an unexpected pregnancy. Investigators shall advise these subjects on the use of adequate methods of contraception and will check for adherence during study visits. Subjects must agree to use adequate contraception during the study and for 28 days after the last dose of study drug.

Methods that can achieve a failure rate of less than 1% per year when used consistently and correctly are considered as highly effective birth control methods. Such methods include:

- Combined (estrogen and progestogen containing) hormonal contraception associated with inhibition of ovulation:
 - Oral
 - Intravaginal
 - Transdermal

- Progestogen-only hormonal contraception associated with inhibition of ovulation:
 - Oral
 - Injectable
 - Implantable¹
- Intrauterine device¹
- Intrauterine hormone-releasing system¹
- Bilateral tubal occlusion¹
- Vasectomized partner^{1,2}
- Sexual abstinence³

Acceptable birth control methods which may not be considered as highly effective – those that result in a failure rate of more than 1% per year – include:

- Progestogen-only oral hormonal contraception, where inhibition of ovulation is not the primary mode of action
- Male or female condom with or without spermicide⁴
- Cap, diaphragm or sponge with spermicide⁴

¹ Contraception methods that are considered to have low user dependency.

² Vasectomized partner is a highly effective birth control method provided that partner is the sole sexual partner of the WOCBP trial participant and that the vasectomized partner has received medical assessment of the surgical success.

³ Sexual abstinence is considered a highly effective method only if defined as refraining from heterosexual intercourse during the entire period of risk associated with the study treatments.

⁴ A combination of male condom with either cap, diaphragm or sponge with spermicide (double barrier methods) are also considered acceptable, but not highly effective, birth control methods

12.5 Clinical Laboratory Tests

Clinical safety laboratory tests (Table 3: Clinical Laboratory Analytes [Table 3](#)) will be conducted by a central or local laboratory according to methods and time points specified in the schedule of assessments (**Table 1**). Analytes for clinical safety laboratory tests are listed in Table 3: Clinical Laboratory Analytes [Table 3](#). The Investigator must review the laboratory report, document this review, and record any clinically significant changes occurring during the study as an AE. The laboratory reports must be filed with the source documents. All laboratory tests with values considered clinically significantly abnormal during participation in the study or after the last dose of study drug should be repeated until the values return to normal or baseline or are no longer considered clinically significant by the Investigator or Medical Monitor. If clinically significant values do not return to normal/baseline within a period judged reasonable by the Investigator, the etiology should be identified, and the Sponsor notified.

Table 3: Clinical Laboratory Analytes

Chemistry	Urine	Other Laboratory Measurements
Sodium Potassium (local lab) Chloride Bicarbonate Magnesium Phosphate Total protein Albumin Calcium Glucose BUN Creatinine eGFR CKD-EPI w/o race Total bilirubin Direct bilirubin AST ALT Alkaline phosphatase Serum aldosterone PRA Serum cortisol Cystatin-C	First Morning Urine Void: Creatinine Albumin Protein Urinalysis, spot urine (central lab): RBCs Glucose Protein Urine pH Ketones Bilirubin Urine specific gravity Blood 24-hour urine*: Albumin Protein Free cortisol Aldosterone Sodium Potassium Creatinine	Hematology - CBC auto differential panel (central lab): Hematocrit Hemoglobin RBC count WBC count Platelet count MCH MCHC MCV Mean platelet volume Red cell distribution width CBC, nucleated red blood cell WBC differential (basophils, eosinophils, immature granulocytes, lymphocytes, monocytes, neutrophils [%], absolute count]) Pregnancy Testing: Serum or Urine Pregnancy (for WOCBP only) FSH (postmenopausal women only) Biomarkers** (central lab): hsCRP NTproBNP NGAL KIM-1 Exploratory biomarkers Other: HbA _{1c} ACTH Stimulation testing

Refer to the Schedule of Assessments (**Table 1**) for collection time points. * An aliquot of urine will be retained for future assessments. **A serum aliquot, a sample of whole blood for proteomic and genomic assessments, and a mid-stream urine sample will be collected and retained for future biomarker analyses.

Abbreviations: ACTH, adrenocorticotrophic hormone; ALT, alanine aminotransferase; AST, aspartate aminotransferase; BUN, blood urea nitrogen; CBC, complete blood count; CKD-EPI, Chronic Kidney Disease Epidemiology Collaboration; eGFR, estimated glomerular filtration rate; FSH, follicle-stimulating hormone; HbA_{1c}, glycosylated hemoglobin; hsCRP, high-sensitivity C-reactive protein; KIM-1, kidney injury molecule-1; MCH, Mean corpuscular hemoglobin; MCHC, Mean corpuscular hemoglobin concentration; MCV, Mean corpuscular volume; NGAL, Neutrophil gelatinase-associated lipocalin; NTproBNP, N-terminal (NT)-pro hormone BNP; PRA, plasma renin activity; RBCs, red blood cells; WBC, White blood cell; w/o, without.

12.6 Definitions and Procedures for AEs and SAEs

12.6.1. Definition of AE

An AE is any unfavorable and unintended sign (including an abnormal laboratory finding), symptom, or disease (new or exacerbated) temporally associated with the use of a study drug or other protocol-imposed intervention, whether or not considered related to the study drug. Any medical condition or clinically significant laboratory abnormality with an onset before the first dose of study drug is considered a pre-existing condition that will be captured as part of the subject's medical history and will not be considered an AE unless the condition worsens in intensity or frequency after study enrollment.

Events meeting the AE definition include the following:

- Any abnormal laboratory test results (hematology, clinical chemistry, or urinalysis) or other safety assessments (e.g., ECG, radiological scans, vital signs measurements), including those that worsen from baseline, considered clinically significant in the medical and scientific judgment of the Investigator (i.e., not related to progression of underlying disease).
- Exacerbation of a chronic or intermittent pre-existing condition including either an increase in frequency and/or intensity of the condition.
- New condition detected or diagnosed after study intervention administration even though it may have been present before the start of the study.
- Signs, symptoms, or the clinical sequelae of a suspected intervention-intervention interaction.
- Signs, symptoms, or the clinical sequelae of a suspected overdose of either study intervention or a concomitant medication. Overdose per se will not be reported as an AE/SAE unless it is an intentional overdose taken with possible suicidal/self-harming intent. Such overdoses should be reported regardless of sequelae.

Events not meeting the AE definition include the following:

- Any clinically significant abnormal laboratory findings or other abnormal safety assessments that are associated with the underlying disease, unless judged by the Investigator to be more severe than expected for the subject's condition.
- The disease/disorder being studied or expected progression, signs, or symptoms of the disease/disorder being studied, unless more severe than expected for the subject's condition.
- Medical or surgical procedure (e.g., endoscopy, appendectomy): The condition that leads to the procedure is the AE.
- Situations in which an untoward medical occurrence did not occur (social and/or convenience admission to a hospital).
- Anticipated day-to-day fluctuations of pre-existing disease(s) or condition(s) present or detected at the start of the study that do not worsen.

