5 Study visit windows (double blind period and run-in) are \pm 3 days.

6 Written informed consent must be obtained prior to conducting any study procedures.

7 At the Screening Visit a physical examination will be performed and should include an evaluation of the cardiovascular, dermatologic, musculoskeletal, respiratory, gastrointestinal, and neurologic systems. Height will be measured at Screening only. At other visits, a limited, symptom-directed physical examination should be performed. Any abnormality identified should be recorded either as medical history or AE accordingly.

8 Serum potassium must be collected 3 days prior to Randomization and values must be reviewed by the Investigator for Randomization eligibility.

9 During Screening, one first morning urine void to be brought in, in the first week after Screening to determine eligibility. An unscheduled visit during Screening period for subjects to return first morning void must take place a minimum of 7 days prior to the Run-in visit so that the result is available for eligibility review. The sample needs to be 200-5000 mg/g inclusive to meet eligibility criteria. Samples will be assessed for albumin, protein, and creatinine.

10 Subjects will be given a 24-hour urine collection kit to take home at preceding visits. An aliquot of urine will be retained for future biomarker assessments.

11 Subjects must start urine collection on Day-1 and return the collected 24-hour urine on Week 0 Randomization visit. 24-hour urine samples will be utilized for assessment of albumin, protein, creatinine, sodium, potassium, cortisol, and aldosterone. An aliquot of urine will be retained for future assessments.

12 Women of childbearing potential only. A sample for serum pregnancy test will be collected at Screening. Follicle stimulating hormone must be used to confirm postmenopausal status in all postmenopausal women at Screening. Urine pregnancy tests will be done at other visits. If urine pregnancy test is positive, a serum pregnancy test will be collected to confirm results at the local lab.

13 All AEs and SAEs will be collected from signing of informed consent form until the subject has completed the EoS visit or transitioned to the open label extension study. All AESIs will be collected upon initiation of treatment until the subject has completed the EoS visit or transitioned to the open label extension study.

14 Only for SGLT2i naïve patient or patient switching to sponsor provided SGLT2i.

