6. STUDY DRUG ADMINISTRATION AND MANAGEMENT

The study drug products for this study are lorundrostat as well as the matching placebo. Additionally, commercially available dapagliflozin will be provided to SGLT2i naïve subjects or those that wish to switch to study provided SGLT2i. Subjects may also choose to stay on their currently prescribed SGLT2i.

The formulation and the manufacturing of study drug follows generally accepted standard procedures. The description, covering in detail all aspects regarding quality and safety of study drug product is part of the Investigator's Brochure (IB) for lorundrostat and product prescribing information for dapagliflozin (FARXIGA®) (FDA Reference ID: 4788803).

■ [REDACTED]

[REDACTED]
[REDACTED]
[REDACTED]
[REDACTED]

[REDACTED]

[REDACTED]	[REDACTED]	[REDACTED]
[REDACTED]	[REDACTED]	[REDACTED]
[REDACTED]	[REDACTED] [REDACTED] [REDACTED] [REDACTED]	[REDACTED]
[REDACTED]	[REDACTED] [REDACTED]	[REDACTED] [REDACTED] [REDACTED] [REDACTED]
[REDACTED]	[REDACTED] [REDACTED] [REDACTED] [REDACTED]	[REDACTED]
[REDACTED]	[REDACTED] [REDACTED] [REDACTED]	[REDACTED] [REDACTED] [REDACTED] [REDACTED]
[REDACTED]	[REDACTED]	[REDACTED]
[REDACTED]	[REDACTED]	[REDACTED]
[REDACTED]	[REDACTED] [REDACTED] [REDACTED]	[REDACTED]

Abbreviations: HBr, monohydrobormide; IMP, investigational medicinal product; QD, once daily.

All packaged tablets will be assigned a unique identifying number, used by the Randomization and trial supply management (RTSM) system to identify the content but maintaining the blind. The test materials will be identified by the lot, batch numbers, retest date, and certificate of analysis.

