8.4.1. Time Period and Frequency for Collecting AE and SAE Information

For subjects rolling over into the OLE, all AEs and SAEs will be collected from signing of the study ICF until just before the first assessment in the OLE study. All AESIs will be collected from Randomization until just before the first assessment in the OLE study. For subjects not participating in the OLE, all AEs and SAEs will be collected from signing of the ICF to 28 days post the last dose of study drug. All AESIs will be collected from Randomization until the EOS visit.

Adverse events that begin before the start of study drug (lorundrostat or placebo) at Randomization, but after obtaining informed consent will not be considered TEAEs.

Under no circumstance should the reporting of SAEs and AESI exceed 24 hours ([Appendix 12.6.4.1](#)). The Investigator will submit any updated SAE data to the Sponsor within 24 hours of it being available.

Investigators are not obligated to actively seek information on AEs or SAEs after the conclusion of study participation (i.e., after the completion of the EoS visit). However, if the Investigator learns of any SAE, including a death, at any time after a subject has been discharged from the study, and he/she considers the event to be reasonably related to the study drug or study participation, the Investigator must notify the Sponsor promptly.

In the event that study drug is interrupted, AEs and SAEs will be collected throughout the interruption. If study drug is permanently discontinued for any reason, the reason will be recorded and the subject should be encouraged to remain in the study so that important safety information can be obtained. All AEs and SAEs leading to discontinuation of study drug or discontinuation of study will be collected. Once a subject withdraws consent to participate in the study, no further information can be collected from the subject.

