6.6.2.1 AEs during the Run-In Period

Any AEs occurring after the first dose of SGL2-i medication in the Run in Period and before the first dose of the investigational medication (lorundrostat/placebo) in the DB period are considered AEs in the Run-In period. This definition also includes worsening of the existing AE during the Run-In period.

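### Protocol 12.6.1 starts AE status at the first dose of study drug, while 8.4.1 and the SAP start it at consent or run-in, so new non-worsening run-in events can be filed either way

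*Protocol*

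**What the plan says.** Protocol 12.6.1 (Definition of AE) says that a medical condition or clinically significant laboratory abnormality "with an onset before the first dose of study drug is considered a pre-existing condition". Such a condition goes into medical history and "will not be considered an AE unless the condition worsens in intensity or frequency after study enrollment". The opening sentence of the same section is wider: it covers unfavorable events "temporally associated with the use of a study drug or other protocol-imposed intervention".

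Protocol 6 says which products are meant: "The study drug products for this study are lorundrostat as well as the matching placebo". Dapagliflozin is described there as an additional supply.

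Protocol 8.4.1 starts collection earlier. For subjects entering the extension, "all AEs and SAEs will be collected from signing of the study ICF"; for the others, "all AEs and SAEs will be collected from signing of the ICF to 28 days post the last dose of study drug". It then says that AEs beginning after consent but before lorundrostat or placebo are not TEAEs, and so still calls them AEs. Footnote 13 of the schedule of assessments (Protocol Table 1, SAP 9.1) also starts at consent.

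SAP 6.6.2.1 assigns to the run-in "Any AEs occurring after the first dose of SGL2-i medication in the Run in Period and before the first dose of the investigational medication". SAP 4.1.2 creates a Run-in Safety Analysis Set. SAP 6.6.2.6 plans a summary of any AE, a summary of run-in AEs and a run-in listing. The notes in SAP 6.6.2.4 use the consent date to decide whether an event is an AE at all.

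**The concern.** The two starting points differ by the whole screening and run-in period. The run-in is when SGLT2i-naive subjects begin study-provided dapagliflozin, and Protocol 2.3.1.5 to 2.3.1.9 commits to monitoring for hypotension, ketoacidosis, acute kidney injury, hypoglycemia and certain infections. The safety endpoint in Protocol 3.2.3 is the incidence and severity of AEs, not of TEAEs only.

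If some sites apply 12.6.1 literally and others apply 8.4.1, the same event will be an AE at one site and medical history at another. The run-in table would then reflect site practice as well as what happened to subjects, and nothing in the output would show which.

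**Working it through.** No design figure rests on this rule, so the check compares passages and then sizes the window.

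**1. Which definition governs.** Protocol 8.4 makes investigators responsible for events that meet the definition in Appendix 12.6, and 8.4.2 sends recording to the same appendix. SAP 6.6.2 takes its AE definition from the protocol. So 12.6.1 decides what enters the AE form and hence the SAP tables; it is not background text.

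**2. When the first dose occurs.** Under Protocol 6 and the parenthesis in 8.4.1, study drug is lorundrostat or placebo, first given at Week 0.

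**3. One case under each passage.** Take a new non-serious event at Week -1, in a subject who began study-provided dapagliflozin at Week -2, that stays stable or resolves.

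| Passage | Starting point | Status of the event |
|---|---|---|
| Protocol 12.6.1, pre-existing conditions | First dose of study drug | Medical history |
| Protocol 12.6.1, opening sentence | Study drug or protocol-imposed intervention | AE |
| Protocol 8.4.1 | Consent | AE, not TEAE |
| Table 1 footnote 13 | Consent | AE |
| Protocol 12.5 (if a clinically significant laboratory change) | During the study | AE |
| SAP 6.6.2.1 | First run-in SGLT2i dose | Run-in AE |
| SAP 6.6.2.4 notes | Consent date | Not ruled out as an AE |
| SAP 6.6.2.2 | First TP1 dose | Not a TEAE |

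**4. The worsening exception.** SAP 5.2 equates enrollment with signing consent. A condition that worsens after that point is an AE under 12.6.1 too. The exception does not reach a new event that never worsens.

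**5. Medical history stays open as a destination.** Protocol 8.1.1 allows it to be updated at later visits, and Table 1 footnote 7 sends examination abnormalities to medical history or to the AE form without a rule for choosing.

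**6. Outputs affected.** The Any-AE summary and the run-in AE summary and listing. TEAE displays start at the first TP1 dose, so this event is outside them under either rule.

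**7. Size of the window.**
- Schedule: 2 (screening) + 2 (run-in) + 4 (TP1) + 4 (washout) + 4 (TP2) + 2 (follow-up) = 18 weeks.
- Consent to first dose: 2 + 2 = 4 weeks; 4/18 = 22%.
- Run-in alone: 2/18 = 11%.
- If screening is extended to 4 weeks, as footnote 1 permits: (4 + 2)/(18 + 2) = 6/20 = 30%.

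**The case against.** The best defense is that sites have ample direction toward the AE form. Protocol 8.4.1 addresses exactly this window, Table 1 marks the AE row at Screening and Run-in, 8.4.2 has AEs sought at every contact, and the opening sentence of 12.6.1 fits dapagliflozin started under the protocol. *Study drug* is also used loosely: Table 1 marks it as dispensed at run-in, with footnote 14 reading "Only for SGLT2i naïve patient or patient switching to sponsor provided SGLT2i", and Protocol 2.3.1.8 uses the term when discussing SGLT2i. On that reading, an event after the first study-provided dapagliflozin dose falls after first dose and is an AE. And an event filed as medical history still appears in the SAP 6.3.3 outputs.

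Much of this stands. Many sites will probably record such events as AEs, and the term is ambiguous. But the looser reading does not cover subjects who keep their own SGLT2i, or events between consent and run-in. Protocol 6 and 8.4.1 point the other way, and no passage says which rule prevails. A medical-history table does not replace a run-in AE table, because it does not separate events that began in the run-in.

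A reader might infer that a serious run-in event would escape SAE reporting. The documents do not support that: 12.6.2 defines an SAE as an untoward occurrence without a first-dose limit, 8.4.1 collects SAEs from consent, and 8.4.6 does the same for fatal events. A reader might also infer that the run-in tables would be nearly empty. That would require every site to disregard 8.4.1 and Table 1.

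**Conclusion.** The conflict is real and should be corrected, but its reach is limited. It affects new, non-worsening events with onset between consent and the first lorundrostat or placebo dose, and mainly non-serious ones. The Any-AE and run-in AE displays may be incomplete and may differ by site. The primary endpoint and the lorundrostat-placebo TEAE comparison do not change under either rule.

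The window is 4 of 18 scheduled weeks, 2 of them run-in. The documents give no AE rate for it and no indication of how sites resolved the conflict, so any count of affected subjects would be a guess. The conclusion assumes that *study drug* carries the meaning in Protocol 6 and 8.4.1; under the looser Table 1 usage the conflict narrows but does not disappear.

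**What to change.** **Protocol.** In 12.6.1, change the onset cut-off from the first dose of study drug to signing of the informed consent form. State that events from consent to the first lorundrostat or placebo dose are AEs or SAEs but not TEAEs. Define study drug once and use it the same way in Section 6, Table 1, 8.4.1 and 12.6.1.

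**SAP.** SAP 1.2 reports that the study was completed under Amendment 3, so new protocol wording alone cannot change what sites recorded. Add to SAP 6.6.2 that medical-history records with onset after consent and before the first TP1 dose will be reviewed or queried. Count them as run-in AEs when they start after the first run-in SGLT2i dose, and otherwise as pre-treatment AEs. Records whose partial onset date cannot be placed relative to consent should be queried.

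**Cost.** A few sentences, some added data review and a few more AE records; no new visits or data fields. The review cannot recover events that were never recorded.
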